3.3 Number of Patients

Up to 20 adult patients with T1DM can be enrolled. The upper bound is based on the expectation that some patients will be excluded after the Screening Visit and the possibility that some patients may have to be discontinued before completion (due to, for instance, inter-current illness or patient withdrawal). It is expected that up to 10 patients will complete the trial protocol.

Clinical Trial Protocol
ZP4207-16051

Version number: 3.0
Amendment 2.0
Date: 03 August 2016

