7.4.1 Visit Procedures

- Patients will be asked to arrive at the visit at least 1 hour in advance of the start of the BP having fasted since 12:00 AM the night before (treatment with simple carbohydrate of up to 30 g for a low is allowed). If the patient is not fasted, the visit will be rescheduled within the visit window. If BG is >250 mg/dL, the visit will be rescheduled within the visit window. If BG is <50 mg/dL, treatment with simple carbohydrate is allowed. If the patient experiences persistent hypoglycemia, the visit will be rescheduled within the visit window. If the visit needs to be rescheduled due to hypoglycemia or hyperglycemia, trial staff will assist the patient with insulin or medication adjustments to address glycemic control. The patient will be instructed to contact trial staff later in the day if his or her BG remains uncontrolled.
- Upon arrival to the visit, the patient's weight and vital signs including body temperature and blood pressure will be documented.
- Patient reports of symptoms, any other complaints, and AEs will be reviewed.
- Concomitant medications will be recorded.
- Chemistry and hematology samples will be collected at visit start (see [Appendix B](#)).
- ADA samples will be collected before the start of dosing (Visit 3 only).
- A 12-lead ECG will be performed.
- A urine HCG pregnancy test will be performed in female patients of childbearing potential. If the test is positive, the patient will be informed of the result and the visit will be ended.
- Patients will complete a baseline survey about their attitudes and experience with their usual diabetes care.
- An intravenous (IV) catheter will be placed for blood sampling.

Clinical Trial Protocol
ZP4207-16051

Version number: 3.0
Amendment 2.0
Date: 03 August 2016

- Trial staff will assist the patient to calibrate their CGM, review the trial procedures again and assist with the setup of the BP system, including inserting and priming infusion sets.
- The control algorithm will be initialized only with the patient's weight. Diagnostics will be performed to ensure that the CGM device is appropriately calibrated and that all of the components of the BP systems are in working order.
- The basal rate of the patient's own insulin infusion pump will be changed to be 2-fold higher than weighted mean of the basal rate during the trial period. This is intended to increase the usage of glucagon during the treatment visit.

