 - >250 mg/dL
 - >300 mg/dL
- Number of severe hypoglycemic events (patients unable to self-treat, requiring the assistance of another person)
- Number of episodes of symptomatic hypoglycemia
- Number of carbohydrate interventions for hypoglycemia
- Total grams of carbohydrates taken for hypoglycemia
- Mean CGM glucose

Clinical Trial Protocol
ZP4207-16051

Version number: 3.0
Amendment 2.0
Date: 03 August 2016

8.2.3 **Non-glycemic**

- Glucagon/ZP4207 total delivery per kg of body mass
- Insulin total delivery per kg of body mass
- Number of unscheduled infusion set replacements
- Number of unscheduled CGM sensor changes

9 **LABORATORY ASSESSMENTS**

Descriptions of sample handling and sample processing, storage, and shipment at the site will be included in the laboratory manual.

The responsible laboratories are listed in the [address list](#).

9.1 **Safety Laboratory Assessments**

Chemistry and hematology samples will be collected at specified time points. See [Appendix A](#) for the schedule of procedures and [Appendix B](#) for a list of clinical laboratory analytes.

9.2 **Pharmacodynamic Assessments (Plasma Glucose)**

At Visit 3 and Visit 4, plasma glucose samples will be taken from the IV at least hourly in parallel with ZP4207/glucagon exposure sampling and measured using the YSI 2300 STAT Plus. If the YSI 2300 STAT Plus and/or IV fails, the Nova StatStrip Xpress will be used for glucose measurements. If BG is <150 mg/dL, then sampling will be every 30 minutes. If BG is <100 mg/dL, then sampling will be every 20 minutes. If BG is <80 mg/dL, then sampling will be every 10 minutes. The actual time of sampling will be recorded in the eCRF.

9.3 **Exposure Assessments (ZP4207 and Glucagon)**

At Visit 3 and Visit 4, ZP4207/glucagon exposure sampling will be collected at least hourly. If BG is <150 mg/dL, more frequent samples for plasma ZP4207/glucagon may be drawn at the discretion of the Investigator. The actual time of sampling will be recorded in the eCRF.

Bioanalytical Reports will be prepared.

9.4 **Anti-drug Antibody Assessments**

Blood samples (including back-up samples) for serum anti-ZP4207 and anti-glucagon antibodies will be taken at Visit 3 and the Follow-up Visit 6.

A Bioanalytical Report will be prepared.

10 **SAFETY REPORTING**

10.1 **Adverse Events**

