11.2.2 Analysis of Efficacy

The analysis of BP function endpoints and glycemic endpoints will be on an intention-to-treat basis. In cases where a treatment arm was not completed (and that arm was not repeated according to protocol criteria), available data from that arm will be used in the data analysis.

The Shapiro-Wilk test will be used to determine the normality of the residuals for each comparison. Summary tables that display descriptive statistics, including percentages, means or medians, and standard deviation and/or ranges, as appropriate, will be provided.

Clinical Trial Protocol
ZP4207-16051

Version number: 3.0
Amendment 2.0
Date: 03 August 2016

A paired t-test or the Wilcoxon signed rank test for comparison of means with normally or non-normally distributed residuals, respectively, will be used. In a secondary analysis, any period effect and any interaction between treatment and period will be looked for, although no such interaction is predicted for the efficacy outcome. Further details will be included in the SAP.

The number of patients and proportions of severe hypoglycemic events, symptomatic hypoglycemia, and carbohydrate interventions due to hypoglycemia with the event counts will be summarized descriptively, and the proportions will be analyzed by a Fisher's exact test if data allow.

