11.2.4 Sample Size Determination

No formal sample size calculations were made. It is expected that between 10 and 12 patients will be randomized in the trial. The sample size is based on a clinical rather than statistical rationale. The sample size is considered adequate to address the primary trial objective of exploring the safety of ZP4207 when used in the iLet and with reference to Lilly glucagon used in the iLet.

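### Symptomatic hypoglycemia and carbohydrate rescues are defined as counts, but section 11.2.2 tests only any-versus-none with an unpaired Fisher test; a paired comparison of the counts would be a cheap improvement

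*Protocol*

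**What the plan says.** Section 8.2.2 (Glycemic) lists among the secondary endpoints "Number of episodes of symptomatic hypoglycemia" and "Number of carbohydrate interventions for hypoglycemia". Both are counts per treatment visit. The same list includes "Total grams of carbohydrates taken for hypoglycemia".

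For severe hypoglycemia, symptomatic hypoglycemia and carbohydrate interventions, section 11.2.2 states that patient numbers and proportions "with the event counts will be summarized descriptively, and the proportions will be analyzed by a Fisher's exact test if data allow". Earlier in the section there is a general rule that is not tied to named endpoints: "A paired t-test or the Wilcoxon signed rank test for comparison of means with normally or non-normally distributed residuals, respectively, will be used". Further detail is deferred to the SAP.

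Every patient receives both products in random order (section 5). On size, section 11.2.4 says "It is expected that between 10 and 12 patients will be randomized in the trial" and section 3.3 says "It is expected that up to 10 patients will complete the trial protocol". Section 11.2.4 also says that no formal sample size calculation was made. No event rate, alpha or power target is given.

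Section 7.4.1 doubles the basal rate of the patient's own pump until exercise starts at about Hour 6 to 7, and explains: "This is intended to increase the usage of glucagon during the treatment visit". A meal bolus from that pump and structured exercise fall in the same visit. Section 7.4.3 allows carbohydrate treatment to be repeated, so one visit can produce several interventions.

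**The concern.** The endpoint and its test are on different scales. The endpoint asks how many events occurred, while the test asks only whether there was at least one. A patient with one rescue on one product and four on the other counts as an event on both, so the difference between one and four is lost.

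This matters more when events are common. The visit adds deliberate extra insulin and then exercise, so it is plausible, though not established, that many patients have an event on both products.

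There is a second fault in the same sentence. Fisher's exact test assumes two independent groups, whereas here each patient appears in both arms.

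At stake is whether the trial's comparison of discrete hypoglycemic events can show a real difference between the two products. The method is written into section 11.2.2, so a SAP that follows the protocol would carry it forward.

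**Working it through.** **No figure to reproduce.** The protocol states no power for any comparison.

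**Inputs from the protocol.** Paired two-period design (section 5); about 10 completers (section 3.3); 10 to 12 randomized (section 11.2.4).

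**Assumed, because the protocol is silent.** Two-sided 5% level; event rate λ per visit on the better product and 2λ on the worse (rate ratio 2); Poisson counts with a gamma patient effect of shape 2 and mean 1, shared by both visits.

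**Step 1: how fast the binary scale saturates.** Under this model P(no event at rate λ) = (1 + λ/2)^-2, and P(no event on either visit) = (1 + 3λ/2)^-2. A pair is informative on the binary scale only if it is discordant:

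P(discordant) = (1 + λ/2)^-2 + (1 + λ)^-2 − 2(1 + 3λ/2)^-2

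| λ (better) | any event, better | any event, worse | event on both | discordant | expected discordant pairs of 10 |
|---|---|---|---|---|---|
| 0.5 | 36% | 56% | 24% | 43% | 4.3 |
| 1 | 56% | 75% | 47% | 37% | 3.7 |
| 2 | 75% | 89% | 70% | 24% | 2.4 |
| 3 | 84% | 94% | 81% | 16% | 1.6 |

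For λ = 2: 0.25 + 0.111 − 2(0.0625) = 0.236.

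**Step 2: what the binary tests need.** With 10 per arm, Fisher gives p = 0.033 for 10/10 versus 5/10, but p = 0.087 for 10/10 versus 6/10 and p = 0.057 for 9/10 versus 4/10. At λ = 2 the expected split is about 9 versus 7.5. Exact McNemar needs at least 6 discordant pairs, all in one direction: 2 × 0.5^6 = 0.031, whereas 2 × 0.5^5 = 0.0625. Only 2.4 are expected. A paired binary test therefore corrects the independence error but does not recover the information.

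**Step 3: simulated power** (10 patients, rate ratio 2, 4,000 trials per cell). The last column adds an independent gamma effect of shape 2 for each visit.

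| λ (better) | Fisher | exact McNemar | signed rank on counts | signed rank, with visit-level variation |
|---|---|---|---|---|
| 0.5 | 3-4% | 3% | 9% | 6% |
| 1 | 3% | 2% | 25% | 12% |
| 2 | 2% | 0.4% | 51% | 21% |
| 3 | 0.4% | 0% | 69% | 26% |

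With visit-level variation Fisher stays at about 1-3%. If that variation is larger (shape 1), signed rank gives about 5%, 10%, 14% and 15%.

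At λ = 0.25 signed rank has 1.8% against 2.6% for Fisher. At λ = 0.15 it has 0.4% against 1.4%. There is no gain there.

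With 12 patients and λ = 1, Fisher has 6% and signed rank 34%.

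The type I error of the signed rank test stayed below 5% in every null case run.

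**The case against.** The strongest objection is that the size of the loss depends on a rate the protocol does not give. This stands. A reader might infer that the design forces hypoglycemia in every patient, so that most of the power is certain to be lost. The documents do not support that. The stated purpose of the doubled basal rate is more glucagon use, and section 1.2 says glucagon may be dosed preemptively, even above range. The earlier outpatient results in section 1.3 show 0.6-1.5% of CGM values below 60 mg/dL on the bionic pancreas, though without a doubled basal rate. If events are rare, every test is weak at this size and the count test is no better.

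Clustering also stands. Treatment can repeat at 15-minute intervals during one low, and rescue below 60 mg/dL is optional, so intervention counts will vary more than Poisson. That cuts the gain by half or more at the higher rates but does not remove it.

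A reader might also infer that the trial would report no difference in hypoglycemia on the Fisher result alone. That does not follow. Percent time with CGM glucose below 60 mg/dL is the exposure measure named in section 2.2. It, the other low-glucose times and total rescue grams lie outside the Fisher sentence, so they fall under the paired rule. The counts would still be tabulated.

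Finally, the general paired rule does not exclude counts, and the SAP could extend it to them. That is possible, but the later, endpoint-specific sentence assigns the counts to description. On the natural reading it governs; otherwise the two sentences conflict and need reconciling.

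**Conclusion.** The point holds at modest importance. Section 11.2.2 tests two count endpoints on an any-versus-none scale, with a test that ignores the pairing. When events are common, this discards most of the information. With 10 patients and a doubling of the rate, Fisher's power is about 0-4% throughout. The gain from testing counts is about 5 points at 0.5 events per visit on the better product. At 1 to 3 per visit it is roughly 20 to 70 points with a shared patient effect only, or about 9 to 25 points if counts also vary by visit. It vanishes at about 0.25 per visit or below. Rates, rate ratio, alpha and variance structure are all assumptions.

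This is not a failure of a promised power. The trial is a feasibility study sized on clinical grounds, the endpoints are secondary, and other hypoglycemia measures keep a paired comparison. Even the better test leaves the comparison underpowered in most of the scenarios above, so an estimate with its interval matters more than the p-value.

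**What to change.** In section 11.2.2, and in the SAP, replace the Fisher test for these two endpoints. Compare the number of symptomatic episodes and the number of carbohydrate interventions through the within-patient difference (ZP4207 minus Lilly glucagon). Use the exact Wilcoxon signed rank test, since the section already names the signed rank test, and give an estimated difference with a confidence interval. Report the proportions with at least one event, and severe hypoglycemia, descriptively only.

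The cost is one sentence. No new data, patients or procedures are needed, because symptomatic episodes are recorded as adverse events (section 10.5) and carbohydrate treatments are recorded with amount and time (section 7.4.3). The downside is little or no gain, and possibly slightly lower power, if events turn out to be rare.

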1.5 Risk/Benefit

While the potential risks are minimal, the findings of this trial may reveal information that can substantially improve medical care for persons with diabetes. Therefore, the overall risk/benefit for patients participating in this trial is assessed as acceptable.

Potential Risks and Discomforts

Trial patients will be informed by the Investigator of the potential risks of ZP4207 and other trial-related procedures before they enter the trial.

In this trial, patients with T1DM will be included to test the safety and efficacy of the iLet using ZP4207 versus the iLet using Lilly glucagon. The cross-over design with inclusion of the same T1DM patients into the 2 treatment arms in a randomized order will allow for a direct comparison of the safety and efficacy of the 2 treatments, based on intra-patient variability only.

Clinical Trial Protocol
ZP4207-16051

Version number: 3.0
Amendment 2.0
Date: 03 August 2016

Patients may experience mild discomfort associated with the insertion of the infusion sets and sensor into the SC tissues. The risk of discomfort due to insertion of infusion sets and sensors is expected to be slightly greater than in their lives outside the trial because more infusion sets will be inserted and a CGM sensor will be inserted. Most patients will use only one infusion set and not all will use a CGM sensor in usual care.

There is a potential risk of hypoglycemia, since recombinant insulin analog will be administered. Due to frequent monitoring of glucose and direct supervision by a registered nurse (RN) or Doctor of Medicine (MD) at all times, the risk of a hypoglycemic episodes leading to significant harm to patients is expected to be substantially lower than their risk during their usual therapy.

There is a risk of hyperglycemia. This risk is expected to be less than the risk during the patients' lives outside of the trial based on data from earlier BP trials and the design of this trial.

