5 ASSIGNMENT TO TREATMENT GROUPS

This trial is an open-label, randomized cross-over trial. Patients who have completed the Screening Visit and meet all of the inclusion and none of exclusion criteria will be enrolled into the trial. All patients will participate in two 1-day treatment arms in random order (iLet using ZP4207 and iLet using Lilly glucagon) according to a pre-generated randomization scheme. Up to 2 patients may participate in the trial per day. The order of the iLet visits will be randomized in blocks of 2 patients.

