A Training Visit will take place before the first treatment visit. Patients will be trained in the insertion and calibration of the Dexcom G4 sensor and trial policies and procedures. Trial staff will verify that the patients have understood the material and are competent to participate safely in the trial. Patients will be instructed concerning diabetes management (e.g., basal insulin rate adjustment by insulin pump) during fasting prior to and between the treatment visits per the medical judgment of the Investigator. Concomitant medications will also be reviewed.

7.4 **Treatment Visits (Visit 3 and Visit 4)**

- Visit 3 will take place at least 48 hours after screening (Visit 1) and no more than 30 days after screening (Visit 1).
- There will be a 24-hour minimum washout between Visit 3 and Visit 4 and a maximum of 3 weeks between Visit 3 and Visit 4.
- Up to 2 patients may participate per day.
- Each patient will participate in 2 treatment visits: one with the iLet using ZP4207 and one with the iLet using Lilly glucagon in a randomized order.
- The night before the treatment visit, patients will place a Dexcom G4 CGM sensor in the abdominal skin and calibrate the sensor when prompted using the provided Nova StatStrip Xpress meter. Patients will be instructed to call if they encounter any difficulty with their CGM.

Clinical Trial Protocol
ZP4207-16051

Version number: 3.0
Amendment 2.0
Date: 03 August 2016

- Patients will be responsible for their own medications other than insulin during the trial. Any medical advice needed by the patients during their participation that is not directly related to BG control should be obtained from them in their usual manner. Patients may take any over-the-counter medications that they wish during the trial, with the exception of any medication containing acetaminophen as that may cause interference with CGM sensing. If patients experience urgent or emergent medical concerns outside the scope of diabetes care and their primary care physicians, they will be taken to the MGH walk-in clinic or emergency room, or if necessary call 911.
- During the trial, patients will not use any recreational drugs or drugs of abuse. The need to take prescription drugs that dull the sensorium, reduce sensitivity to symptoms of hypoglycemia, or hinder appropriate decision-making may be grounds for exclusion from the trial or discontinuation of participation, a decision that will be made by the Investigator.

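### Section 11.2.2 compares the hypoglycemia and carbohydrate-intervention proportions with Fisher's exact test, which ignores that the same patients are in both arms of the cross-over

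*Protocol*

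**What the plan says.** The design is paired throughout. Section 5 states "This trial is an open-label, randomized cross-over trial" and "All patients will participate in two 1-day treatment arms in random order". Section 7.4 repeats it: "Each patient will participate in 2 treatment visits: one with the iLet using ZP4207 and one with the iLet using Lilly glucagon". Section 1.5 justifies the design as allowing a "direct comparison of the safety and efficacy of the 2 treatments, based on intra-patient variability only".

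Section 11.2.2 (version 3.0, Amendment 2.0) follows this for the continuous endpoints: "A paired t-test or the Wilcoxon signed rank test for comparison of means with normally or non-normally distributed residuals". The next paragraph takes the outcomes "severe hypoglycemic events, symptomatic hypoglycemia, and carbohydrate interventions due to hypoglycemia", summarizes patient numbers, proportions and event counts descriptively, and adds that "the proportions will be analyzed by a Fisher's exact test if data allow". It describes no paired form and no analysis by sequence.

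On size, Section 11.2.4 states that "It is expected that between 10 and 12 patients will be randomized in the trial". The protocol gives no significance level, power or p-value for this test.

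**The concern.** Fisher's exact test on two treatment proportions assumes that the patients in one row are different people from those in the other. Here they are the same 10 to 12 people. The test sees how many patients had an event on each drug, but not whether they were the same patients. It therefore discards the within-patient information that Section 1.5 gives as the reason for a cross-over, and it departs from the paired approach taken one paragraph earlier.

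At stake is the p-value attached to three hypoglycemia outcomes, in a trial of a drug whose role in the device is to prevent hypoglycemia. With so few patients, one patient's pairing can move the correct p-value from one side of 0.05 to the other, and Fisher's test cannot register that.

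**Working it through.** There is no protocol figure to reproduce, because no calculation is stated for this test.

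**Inputs.** From the protocol: n = 10 or 12, with one yes/no outcome per patient per drug. Assumed, because the protocol does not give them: two-sided 0.05, null event rates of 0.1 to 0.5, and a range of within-patient correlations r.

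**Step 1: the two tests on the same data.** Let b and c be the numbers of patients with an event on one drug only (the discordant patients). Exact McNemar is the two-sided binomial test of b against c with probability 1/2. Fisher uses only the two marginal counts.

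- 7/10 versus 1/10, Fisher: 8 events in 20 visits. The tail is [C(10,7)·C(10,1) + C(10,8)·C(10,0)] / C(20,8) = (1200 + 45)/125970 = 0.0099; doubled, 0.0198.
- 7/10 versus 1/10, McNemar: if the one patient with an event on the second drug also had one on the first, the split is 6:0 and p = 2·(1/2)^6 = 0.0312. If not, it is 7:1 and p = 2·(1 + 8)/2^8 = 0.0703.
- 5/10 versus 0/10: Fisher is 2·C(10,5)/C(20,5) = 2·252/15504 = 0.0325. McNemar (5:0) is 2·(1/2)^5 = 0.0625.

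Further tables:

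| Table | Fisher | Exact McNemar |
|---|---|---|
| n=10, 8 vs 2 | 0.0230 | 0.0312 (6:0), 0.0703 (7:1), 0.1094 (8:2) |
| n=10, 10 vs 4 | 0.0108 | 0.0312 (6:0) |
| n=12, 7 vs 1 | 0.0272 | 0.0312 (6:0), 0.0703 (7:1) |
| n=12, 9 vs 3 | 0.0391 | 0.0312 (6:0) |

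The last row shows that Fisher's p-value can also be the larger of the two, but both values there are below 0.05. Going through every possible paired table for n = 10 to 12, none is significant at 0.05 by exact McNemar and not by Fisher. A flip therefore goes only from significant by Fisher to non-significant by McNemar.

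**Step 2: the true level of each test.** With the same event rate p on both drugs, the chance of an event at both visits is p² + r·p(1−p). Summing over all multinomial outcomes gives these probabilities of p ≤ 0.05 (Fisher / exact McNemar):

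| | r = −0.3 | r = 0 | r = 0.3 | r = 0.6 |
|---|---|---|---|---|
| n=10, rate 0.3 | 0.0269 / 0.0113 | 0.0119 / 0.0051 | 0.0031 / 0.0012 | 0.0003 / 0.0001 |
| n=12, rate 0.5 | 0.0467 / 0.0197 | 0.0228 / 0.0135 | 0.0068 / 0.0053 | 0.0006 / 0.0005 |

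At zero or positive correlation Fisher's level is 0.023 or less for n = 10 and 12 at event rates 0.1, 0.3 and 0.5. It passes 0.05 only at strong negative correlation, for example 0.058 at n = 12, rate 0.5, r = −0.43; at n = 10, rate 0.5, r = −0.6 it is still 0.0495. The level is thus set by a correlation that the test does not model.

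**The case against.** The tempting stronger reading is that Fisher's test will produce false positives, or that its p-values are as likely to be too small as too large. Step 2 does not support either. Exceeding 0.05 needs a patient who has an event at one visit to be markedly less likely to have one at the other, and nothing in the protocol suggests that; Section 7.4.1 keeps the meal and its timing the same at both visits. The tables that flip also partly reflect how coarse exact McNemar is: it rejects no more often than Fisher in any scenario tried. This part of the objection stands.

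It is also fair that these are secondary endpoints. The primary endpoint is safety and tolerability (Section 8.1), the glycemic measure named in the objectives is percent time below 60 mg/dL (Section 2.2), which is continuous, and the proportions are summarized descriptively first and tested only if the data are sufficient. No decision in the protocol rests on these p-values. This limits the severity.

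Two further defences do not hold. Section 11.2 leaves specific details to the SAP, but here the protocol names a test outright, and moving from an independent-groups test to a paired one changes the method. And Fisher's test can be valid in a cross-over when applied to discordant patients by sequence (Mainland-Gart), but the text says that the proportions are tested and describes no such table.

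**Conclusion.** The point holds as a mis-specified secondary analysis. Fisher's test on the treatment proportions does not fit a design in which each patient appears in both arms, and it is inconsistent with the paired tests in the same section. The discrepancy is material for individual results (0.020 against 0.070, or 0.033 against 0.063), and where it changes the reading at 0.05 it does so in one direction only. A reader might infer a general inflation of type I error; at zero or positive within-patient correlation the opposite is true, and the test is very conservative. The significance comparisons rest on an assumed two-sided 0.05, and the levels on the assumed event rates and correlations. The point should be fixed, but it does not affect the primary safety conclusion.

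**What to change.** In Section 11.2.2, replace Fisher's test on the treatment proportions with the exact McNemar test on discordant patients. Alternatively use the Mainland-Gart form by sequence, which allows for the period effect that the section already plans to examine. Report the discordant-patient table and the paired difference in proportions with a 95% CI. Make the same change in the version 3.0 synopsis if it repeats the sentence; that synopsis is not in the pages available, so this could not be checked.

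The cost is one sentence before database lock, with no change to patients, visits or data. The downside is that exact McNemar is itself conservative. It cannot reach p < 0.05 with fewer than six discordant patients, and with exactly six all must point the same way (6:0 gives 0.0312, 5:0 gives 0.0625). The gain is a p-value and an estimate that match the design, not more power.
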